Retrograde analysis of data of all patients presented to Aboul Reesh uveitis clinic taking biologics from January 2017- January 2020. In our hospital, the rationale for using biologics was a high frequency of sight-threatening, frequent recurrences of uveitis or intolerance to steroids or other immunosuppressive drugs, with severe adverse reactions.

Sample size:

It is expected to review 250 patients files of Aboul Reesh uveitis clinic to find all JIA patients with ocular inflammation treated with biologics.

Inclusion criteria

1. Both genders
2. Age up to 16 years
3. Diagnosed JIA according to rheumatological criteria with ocular affection
 - Any type of arthritis (oligoarticular, polyarticular, systemic onset, ocular JIA)
 - ANA positive or negative
4. Uncontrolled uveitis or frequent relapses

Exclusion criteria:

1. Patients without definitive diagnosis as JIA

2. JIA patients on biologics without ocular affection (for systemic control) or with uveitis controlled without the use of biologics
4. Patients without adequate duration for follow-up (less than 3 months) or lost follow up data
5. Patients without available data prior to the start biologics (to compare control of the uveitis)

Methodology

Data will be obtained from by retrospective analysis of all files of patients with JIA from the Abou El Reesh ophthalmology outpatient clinic.

The patients with ocular inflammation treated by biologics will be further analyzed.

The data analyzed will divided into pre and post biologic treatment:

In both we will document-

-Baseline BCVA (in logMar notation)

- Grading of ocular inflammation

(Anterior chamber and vitreous cells were graded as +0.5, +1, +2, +3 and +4 according to the guidelines of the Standardization of Uveitis Nomenclature Working Group)

- Number of relapses in one year

- Development of sight threatening complication

- Dose and frequency of systemic, regional and topical steroids

- Other interventions required

Treatment parameters to be analyzed include type, duration and dose of biologic agent used, time taken to reach inflammation control, adverse effects, and time taken to develop those adverse effects.

Improvement or worsening of activity of inflammation was assessed according to the Standardization of Uveitis Nomenclature Group's directions (2 step improvement or worsening of cells/flare)

Treatment was determined as efficacious if one of the following was fulfilled:

1. No relapses or decrease in the number of relapses

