2. Decrease in dose of topical or systemic steroids
3. Improvement of BCVA of at least two lines

Statistical analysis plan:

All data will be entered into Excel spreadsheets (Microsoft Corporation, Redmond, WA, USA). All statistical analyses will be performed using IBM SPSS version 22.0 software (IBM Corp., Armonk, NY, USA). Descriptive statistics will be summarized as the mean \pm standard deviation for numerical data, frequencies and percentages for categorical data. The ANOVA -test and Pearson moment correlation will be used to compare the means for the numerical data and to identify correlations between them. Chi-square test will be used to compare categorical data. P-values ≤ 0.05 will be considered statistically significant.

References

- 2) Qian Y, and Nisha R. (2010) Juvenile Idiopathic Arthritis Associated Uveitis. *Curr Opin Ophthalmol.* 21(6): 468–472. doi:10.1097/ICU.0b013e32833eab83

Retrospective Analysis of the Use of Biologics for Juvenile Idiopathic Arthritis Related Uveitis in Abou El Reesh Pediatric Hospital, Cairo University

First version, 1st march 2020

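### No unit of analysis is set for eye-level outcomes; if both eyes are entered as separate rows, between-child and per-eye change tests give too many false positives

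*Combined protocol and SAP*

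**What the plan says.** The Methodology section sets up a before-and-after comparison: "The data analyzed will divided into pre and post biologic treatment". Two items recorded in each period are measured separately in each eye: "Baseline BCVA (in logMar notation", and inflammation, where "Anterior chamber and vitreous cells were graded as +0.5, +1, +2, +3 and +4". The same list holds items that belong to the child (systemic steroid dose) and items that may belong to either (topical and regional steroids, sight-threatening complications). No sentence says right eye, worse eye, mean or both. The subjects are described as patients, and eyes are never named as a unit.

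The efficacy rule, also under Methodology, needs any one of three criteria. One is "Improvement of BCVA of at least two lines", without saying which eye must gain. Another covers topical or systemic steroid dose.

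The Statistical analysis plan says of numerical data "The ANOVA -test and Pearson moment correlation will be used to compare the means for the numerical data" and of the rest "Chi-square test will be used to compare categorical data", with "P-values ≤ 0.05 will be considered statistically significant". No paired, repeated-measures, mixed-model, GEE or McNemar form is named. The planned summaries are mean with SD, frequencies and percentages. The Sample size section gives 250 files to be reviewed, but no number of children or eyes to be analysed.

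**The concern.** Two eyes of one child share the disease, the biologic and the follow-up, so their values are likely to be correlated. In their standard form the three named methods count every row as independent. A child with both eyes affected who contributes two rows is then treated as two independent observations.

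Vision and control of ocular inflammation are central to the study's aim, so p-values for its main outcomes are at stake. The open unit also affects the efficacy classification, whatever test is used: a child with one eye that gains two lines and one that does not has no defined result on the BCVA criterion. Because this is a file review, the choice could be made after the data have been seen.

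**Working it through.** The plan has no power calculation or precision figure to reproduce; 250 is a screening count. The check therefore asks what the named tests would do if both eyes were entered.

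**Inputs.** From the documents: threshold 0.05, taken as two-sided because sidedness is not stated. Assumptions, because the documents give none: share of children contributing two eyes *b* = 0.5 to 1; between-eye correlation *rho* = 0.3 to 0.8; same-eye pre/post correlation *r*; cross-eye pre/post correlation *c*; 30 or 60 children in the simulations.

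**1. Comparisons between children (for example by type of biologic), with both eyes as rows.** The size-weighted mean number of eyes per child is (1 + 3*b*)/(1 + *b*), so

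design effect = 1 + 2*b*·*rho*/(1 + *b*)

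true type I error = 2·(1 − Φ(1.96/√design effect))

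| *b* | *rho* | Design effect | Type I error | SE understated by |
|---|---|---|---|---|
| 0.5 | 0.3 | 1.20 | 7.4% | 8.7% |
| 0.5 | 0.5 | 1.33 | 9.0% | 13.4% |
| 0.5 | 0.8 | 1.53 | 11.4% | 19.2% |
| 1 | 0.3 | 1.30 | 8.6% | 12.3% |
| 1 | 0.5 | 1.50 | 11.0% | 18.4% |
| 1 | 0.8 | 1.80 | 14.4% | 25.5% |

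At *rho* = 0 there is no inflation.

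Simulation (20,000 runs, 30 and 60 children, all bilateral, *rho* 0.3 to 0.7) gives 8.4% to 13.9% for ANOVA, 8.5% to 13.8% for Pearson correlation with a child-level factor, and 7.6% to 11.4% for chi-square. With the mean of the two eyes as one value per child, the ANOVA comparison returns to 4.8% to 5.1%.

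**2. Pre versus post, paired within each eye but ignoring the child.** The correlation between the two eyes' changes is (*rho* − *c*)/(1 − *r*). For all-bilateral data the design effect is 1 plus that correlation. Correlations of change of 0.50 to 0.71 give 11.0% to 13.4% by formula, and 10.8% to 14.2% by simulation with 30 children. A paired test on the child's mean change gives 4.9% to 5.2%.

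**3. Pre versus post by ordinary unpaired ANOVA, with both eyes as rows.** The between-eye correlation raises the true variance, and the ignored pre/post correlation lowers it. The ratio of true to assumed variance is V = 1 + *rho* − *r* − *c*.

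| *rho*, *r*, *c* | V | Type I error |
|---|---|---|
| 0.7, 0.3, 0.2 | 1.20 | 7.4% |
| 0.5, 0.3, 0.15 | 1.05 | 5.6% |
| 0.5, 0.5, 0.25 | 0.75 | 2.4% |
| 0.5, 0.6, 0.3 | 0.60 | 1.1% |
| 0.7, 0.7, 0.5 | 0.50 | 0.6% |

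When *r* + *c* exceeds *rho*, the test gives too few false positives.

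**4. Is the worse eye at baseline a safe one-eye rule?** Choosing an eye on its baseline value builds in regression to the mean. With no true change and equal variances, the expected false improvement in SD units is (1 − *rho* − *r* + *c*)/√(π(1 − *rho*)). For 0.5, 0.5, 0.25 this is 0.25/√(1.571) = 0.20 SD. Simulated type I error of a paired t-test is then 14%, 19% and 35% with 20, 30 and 60 children. For 0.7, 0.7, 0.5 it is 8.5%, 11% and 18%. This can equal or exceed the inflation being corrected. The child mean avoids it.

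**The case against.** The strongest defence is that the plan speaks of patients throughout and never says that both eyes will be entered. A reader might infer that it treats the eyes as independent rows; the documents do not say so. This stands. The defect is that the unit is open, and the error rates apply only if both eyes are used.

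The defence can add that ANOVA is unqualified, so a repeated-measures form with a subject term is not excluded. This also stands, but it confirms that the text settles neither clustering nor pairing.

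A reader might further infer that the plan's p-values are in general biased towards significance. The third calculation does not support that: for the main before-and-after comparison, an unpaired ANOVA falls below 5% in three of the five scenarios. Nor can one say that the plan's confidence intervals are too narrow, because none are planned. The standard-error figures would carry over to intervals only if these were added.

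What the defence does not answer is that nothing in the plan prevents both eyes from being entered, and that the BCVA criterion is undefined for a child whose two eyes diverge.

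**Conclusion.** The point holds in conditional form. The unit of analysis for eye-level outcomes is unstated, and the named methods make no provision for two eyes of one child or for pre/post pairing. If both eyes are entered as separate rows, false positives rise to about 7% to 14% at nominal 5%, and standard errors are understated by about 9% to 25%. This applies to between-child comparisons, correlations with child-level factors and per-eye paired tests. The figures rest on an assumed bilateral share of 50% to 100% and an assumed between-eye correlation of 0.3 to 0.8 (for paired tests, the correlation of change). For an unpaired pre/post ANOVA the p-value is unreliable but its direction cannot be stated. This should be settled before analysis, because a better method is available at almost no cost.

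**What to change.** - **Name the unit for each outcome.** Use the eye for BCVA and cell grades and, where recorded by eye, for topical or regional steroids and complications. Use the child for systemic steroids, adverse effects and the efficacy classification.
- **Analyse eye-level outcomes** with a mixed model or GEE clustered on the child that also models pre/post pairing. Both are available in the named software.
- **If there are too few children for that,** use one value per child, the mean of the affected eyes, in a paired pre/post test. Do not select the worse eye at baseline.
- **State in advance how two eyes are combined** for the two-line BCVA criterion.

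The cost is a few sentences in the SAP and a different procedure in the software, with BCVA and grades entered by eye. Under the same assumptions, standard errors for between-child and per-eye change comparisons become about 10% to 34% larger (√1.20 = 1.10; √1.80 = 1.34) than in an analysis that counts eyes as independent.

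### Relapses are counted over one year, but 3 months of follow-up qualifies, no minimum pre-biologic period is set, and efficacy criterion 1 has no rule for shorter records

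*Combined protocol and SAP*

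**What the plan says.** The Methodology section divides the data into pre- and post-biologic periods and lists, for both, "Number of relapses in one year". The population is patients "taking biologics from January 2017- January 2020". No data cut-off date is given, and the text does not say that treatment had to start within those dates.

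Two exclusion criteria bear on observation time. One removes "Patients without adequate duration for follow-up (less than 3 months) or lost follow up data", without saying from which date the 3 months run. The other removes "Patients without available data prior to the start biologics (to compare control of the uveitis"), with no minimum length.

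The efficacy rule reads "Treatment was determined as efficacious if one of the following was fulfilled", and its first item is "No relapses or decrease in the number of relapses". That item does not restate the one-year window and has no provision for shorter records. Treatment parameters to be analysed include "type, duration and dose of biologic agent used" and "time taken to reach inflammation control", but neither is linked to the relapse count.

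The statistical analysis plan names ANOVA and Pearson correlation for numerical data and chi-square for categorical data. Nothing in it uses time at risk.

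**The concern.** The follow-up that qualifies a patient is a quarter of the window over which relapses are counted (3/12), and on the pre-biologic side there is no floor at all. A one-year count therefore need not exist on either side. Where the two sides differ in length, a raw comparison favours whichever was watched for less time: a short post record makes the drug look effective, and a short pre record makes it look ineffective.

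Any one criterion suffices, so this passes directly into the proportion called efficacious. A comparison of mean relapse counts carries the same distortion.

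**Working it through.** The plan contains no relapse rate, follow-up distribution or power calculation, so there is no figure of its own to reproduce. The gap itself is read from the text; the arithmetic only shows its size.

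**Assumptions.** Relapses are Poisson, at 1, 2, 3 or 4 per year, with the same rate before and after (no drug effect) and independent counts.

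**Per patient.** P(criterion 1) = P(post = 0 or post < pre).

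Example at 2 per year, 12 months pre and 3 months post (means 2 and 0.5):

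- post = 0: exp(-0.5) = 0.607
- post = 1 and pre ≥ 2: 0.303 × 0.594 = 0.180
- post = 2 and pre ≥ 3: 0.076 × 0.323 = 0.024
- post = 3 and pre ≥ 4: 0.013 × 0.143 = 0.002
- total 0.813

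| Months pre / post | 1/yr | 2/yr | 3/yr | 4/yr |
|---|---|---|---|---|
| 12 / 12 | 48% | 42% | 42% | 43% |
| 12 / 3, raw count | 83% | 81% | 85% | 88% |
| 12 / 3, annualised | 78% | 62% | 54% | 51% |
| 3 / 12, raw count | 38% | 16% | 9% | 5% |

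Annualising is only a partial repair, because zero relapses in 3 months is still zero when multiplied by four. At 2 per year, 0.607 of the 0.623 comes from that limb.

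**Cohort, count capped at one year.** Assume post follow-up is uniform over 3–36 months. Even start dates across the three-year window, with data closing at its end, would give this. The share with under 12 months is (12 - 3)/(36 - 3) = 9/33 = 27%. Differences from full years on both sides, in percentage points:

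| Pre-biologic record | 1/yr | 2/yr | 3/yr | 4/yr |
|---|---|---|---|---|
| Full year for everyone | +4.3 | +4.9 | +5.5 | +6.1 |
| Varies likewise, independently | +2.9 | +1.3 | +0.6 | +0.4 |
| Pre and post share the 36 months | +1.8 | -1.2 | -2.6 | -3.1 |

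The first row becomes +6.8 to +9.7 if follow-up runs only to 24 months, and +2.5 to +3.6 if it runs to 60.

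**Composite.** If a proportion q meets criterion 2 or 3 independently of criterion 1, the difference is multiplied by (1 - q). For the first row, q = 0.3, 0.5 and 0.7 give about 3.0–4.3, 2.1–3.0 and 1.3–1.8 points.

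**Mean count, full pre year, capped post count.** Patients with under 12 months average 7.5 months. With no effect, the ratio of raw means is 1 - 0.273 × (1 - 7.5/12) = 0.898, an apparent 10% fall. A true halving gives 0.449, an apparent 55% fall. If both sides vary alike, the ratio is undistorted.

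**Limit of a person-time rate.** A rate ratio removes the effect of unequal time only if the underlying rate is constant. Entry requires uncontrolled uveitis or frequent relapses. Suppose each patient has one index flare just before start, plus 2 relapses a year throughout, and no drug effect. With 12 months each side the ratio is 2/(1 + 2) = 0.67. With 3 months pre it is 2/[(1 + 0.5)/0.25] = 2/6 = 0.33.

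**The case against.** The strongest reply is that the documented variable is already a one-year count and that the relapse number in criterion 1 naturally refers back to it. That deals with patients who have more than a year. It does nothing for those with less, whom the exclusions admit. Reading the variable as an annualised rate has no support in the text and leaves the zero limb unrepaired.

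The reply does defeat a stronger reading. A reader might infer that post-biologic relapses are counted over all available follow-up, up to three years. Under the follow-up assumed above and a full pre year, criterion 1 would then fall by 12 to 15 points, and a drug that halves relapses would show only a 19% fall in the mean count (0.5 × 19.5/12 = 0.81). The documents do not support this, because the variable is named as a one-year number in both periods.

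It is also fair to say that the cohort effect on the capped reading is small, that the 81–88% figures describe one extreme pattern (a full pre year and exactly 3 months after), and that the follow-up distribution is assumed. Patients already on treatment before 2017 could have longer records. All of this stands and limits the weight of the point. So does the observation that 42–48% meet criterion 1 with no drug effect even when both years are complete. That is a separate weakness, and equal windows do not cure it.

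**Conclusion.** The point holds and should be fixed before analysis. The one-year count, the 3-month eligibility limit and the absence of a pre-biologic minimum do not fit together, and criterion 1 gives no rule for the patients caught between them.

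For an individual short-record patient the effect is large in either direction. For the cohort it is about -3 to +6 points on criterion 1 with follow-up uniform over 3–36 months, up to +9.7 if follow-up is shorter and pre records are complete, and less in the composite. These sizes rest on assumed rates, a Poisson model and assumed follow-up. Even the sign cannot be settled from the documents, so the plan should not be described as biased in favour of biologics on this ground.

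**What to change.** 1. **Criterion 1.** Restrict it to patients observed for at least 12 months on each side. Suggested wording: *In patients with at least 12 months observed before and after biologic start: no relapses in the first 12 months after start, or fewer than in the 12 months before.* Report how many patients are not evaluable and why. The restricted result is unbiased only if short observation is unrelated to outcome, so add a simple sensitivity analysis counting the non-evaluable as failures, then as successes.
2. **Relapse counts.** In place of raw mean counts, report relapses per person-time before and after: a rate ratio with 95% CI, paired within patient, with a log person-time offset (Poisson or negative binomial). Make the 12-month-each-side set the main comparison and all patients a sensitivity analysis, because selection on active disease inflates the pre-biologic rate, most of all in short pre records. Give median and range of months observed on each side, and state that equal windows do not remove regression to the mean.
3. **Composite.** Report the three criteria separately as well as the composite.

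**Cost.** The changes are to the wording of criterion 1 and the analysis plan. Start and follow-up dates are already needed for the 3-month exclusion and the time to inflammation control. Relapse dates must be extracted, and the documents do not say that the files record them.

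Fewer patients will be evaluable for criterion 1. Under the assumed 3–36 months, 27% are lost on the post side alone. If the pre side varies likewise, (24/33)² = 53% remain; if both sides share the 36 months, 12/33 = 36% remain. The gap between the two sensitivity results equals the share not evaluable: 27, 47 or 64 points. In the last two cases the bounds would say little, and the report should acknowledge that.

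### Sight-threatening complications are compared before and after the biologic with no window lengths and no rule for eyes already affected, so unequal observation time can set the sign of the difference

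*Combined protocol and SAP*

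**What the plan says.** The Background and introduction of the combined protocol and SAP makes preventing sight-threatening complications part of the aim, to be weighed against side effects. In the Methodology section the data are split at the start of the biologic, and the same items are recorded on each side. The whole specification of this outcome is "Development of sight threatening complication". The line just above it has a time base: "Number of relapses in one year".

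The window lengths are not settled elsewhere:
- Population of study identifies patients "taking biologics from January 2017- January 2020". It does not say whether pre-biologic data may come from before January 2017.
- The Exclusion criteria remove "Patients without adequate duration for follow-up (less than 3 months) or lost follow up data", which sets a minimum for follow-up but no maximum.
- They also remove "Patients without available data prior to the start biologics (to compare control of the uveitis", which requires some earlier data but no duration.

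For analysis, the Statistical analysis plan gives "frequencies and percentages for categorical data" and states "Chi-square test will be used to compare categorical data". It assigns no test to this item, so use of the chi-square here is inferred. The three efficacy criteria that close the Methodology section (relapses, steroid dose, visual acuity) do not include complications.

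**The concern.** A percentage of eyes developing a complication depends on how long the eyes were watched and on how many could still develop it. If the two windows differ in length, the percentages differ even when the risk per year is unchanged. If an eye can develop a given complication only once, an eye affected before the biologic cannot contribute again afterwards, yet nothing removes it from the later denominator. The first effect can push the comparison either way. The second lowers the later percentage.

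What is at stake is the prevention aim. A reported fall could be read as prevention, or a rise as harm, when either may come from the observation time in the files.

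**Working it through.** **Plan's own figure.** There is none to reproduce. The plan gives no complication rate per year, and the 250 in the Sample size paragraph is a number of files to screen.

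**Inputs from the documents.** Minimum follow-up 3 months; no minimum duration of earlier data; a calendar period of 3 years; 28–67% of patients developing ocular complications (Background), with no time horizon.

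**Assumptions.** Constant hazard h, the same before and after (no drug effect); first events only; all eyes in both denominators; window lengths P (pre) and Q (post) adding to 3 years. Two hazards are used:
- h = 0.2 per eye-year, chosen for illustration.
- h = 0.066, from reading the 28% as reached over an assumed 5 years: −ln(0.72)/5 = 0.066. On the same reading 67% gives −ln(0.33)/5 = 0.222, so 0.2 is near the top of that range. These are per-patient figures, applied to eyes only as a guide.

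**Formulas.** Pre proportion = 1 − exp(−hP). Post proportion over all eyes = exp(−hP) × (1 − exp(−hQ)).

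**Worked case, h = 0.2, P = 2, Q = 1.** Pre = 1 − exp(−0.4) = 0.330. Post = exp(−0.4) × (1 − exp(−0.2)) = 0.670 × 0.181 = 0.122.

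| Years pre / post | h = 0.2: pre vs post | h = 0.066: pre vs post |
|---|---|---|
| 2 / 1 | 33.0% vs 12.2% | 12.3% vs 5.6% |
| 1.5 / 1.5 | 25.9% vs 19.2% | 9.4% vs 8.5% |
| 1 / 2 | 18.1% vs 27.0% | 6.4% vs 11.5% |

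The sign reverses between the first and last rows at both hazards, with no drug effect in either. In the equal-window row the difference comes only from keeping affected eyes in the later denominator. It is 6.7 points at 0.2 and 0.9 points at 0.066.

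**Does incidence among eyes at risk remove this?** Count first onsets only in eyes that have never had the complication by the window start, and stop eye-time at onset. With one shared hazard, the pre rate is (1 − exp(−hP)) divided by (1 − exp(−hP))/h, which equals h. The post rate is also h, so the ratio is 1.00 for any windows.

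**What remains if eyes differ in risk.** Take gamma-distributed hazards with mean 0.2 and coefficient of variation CV; k = 1/CV², θ = 0.2/k, and the share still free at time t is L(t) = (1 + θt)^(−k). Each rate is the fall in L over the window divided by the integral of L over it. For CV = 1 and 2/1 years:
- L(2) = 0.714 and L(3) = 0.625.
- Eye-time per eye enrolled is ln(1.4)/0.2 = 1.682 pre and ln(1.6/1.4)/0.2 = 0.668 post.
- Pre rate = 0.286/1.682 = 0.170. Post rate = 0.089/0.668 = 0.134. Ratio = 0.79.

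Across the three splits the ratio is 0.87 to 0.88 for CV 0.71 and 0.79 for CV 1, again with no drug effect. These values depend on excluding eyes that have ever had the complication. If every affected eye re-entered as at risk when the biologic started, the same hazards would give 0.93 to 1.08. The rule must therefore say which is meant.

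**The case against.** The strongest case on the other side is that this is a short retrospective chart review, complications are not an efficacy criterion, no test is assigned to them, and they may only be described. That stands as a limit on importance. It does not remove the problem, because descriptive percentages ignore observation time just as the chi-square does.

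The numbers rest on chosen hazards and windows. That also stands: at a low hazard with equal windows the artefact is close to negligible. The argument needs clearly unequal windows, which the plan permits but does not impose.

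Four stronger readings are tempting and not supported:
- A reader might infer that the missing unit (eye or patient) also drives the sign. It should be stated, but no calculation here shows that it does so.
- A reader might infer that old complications are carried forward, so that the post figure could never be the lower one. The word development, recorded separately for each period, more naturally means new onsets.
- A reader might infer that the efficacy conclusion is undermined. None of the three criteria uses this item.
- A reader might infer that an at-risk rate ratio would then show prevention. The heterogeneity result above argues against that, and so does selection. The stated reasons for treatment begin "the rationale for using biologics was a high frequency of sight-threatening, frequent recurrences of uveitis". A noun is missing after sight-threatening, so selection on complications is an apparent meaning; selection on recurrences is explicit.

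**Conclusion.** The point holds in a limited form. With no window lengths, no at-risk rule and only percentages or a chi-square, the plan as written can produce a pre/post difference of either sign when nothing has changed. For splits of 2/1 and 1/2 years the spurious differences run from 21 points in favour of the drug to 9 points against it at a hazard of 0.2, and about 7 points in favour to 5 against at 0.066. With equal windows they shrink to about 7 points and 1 point, both in favour. All of this assumes a constant hazard, first events only, all eyes in both denominators and a 3-year total; the documents supply none of the rates or actual windows. The consequence is confined to interpreting the prevention aim. This is a cheap improvement, not a flaw in the efficacy analysis.

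**What to change.** In the SAP:

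1. List the qualifying complications and state the unit. If it is the eye, cluster confidence intervals on patient.
2. Define both windows. Pre: first recorded visit to biologic start. Post: biologic start to one stated end, such as last visit or data cut-off, with a stated rule for how time after a discontinuation or switch is counted in the analysis. Say whether pre data may predate January 2017.
3. In each window count the first onset of each type only among eyes that have never had that type by the window start, with time stopping at onset or window end. Report complications present at the first visit, or with no datable onset, as baseline only.
4. Report window lengths and incidence per eye-year with confidence intervals, in place of a chi-square on pre/post proportions, and keep this descriptive.
5. State as limitations that patients appear to have been partly selected for biologics on sight-threatening problems and on frequent recurrences, and that eyes never affected by biologic start tend to be lower-risk. A lower post rate is therefore not proof of prevention.

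Cost: SAP wording, plus extraction of onset dates and observation time from files already under review. Onsets that cannot be dated are lost to the comparison, and intervals will be wider.
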